10.2.1. Dose Interruption Safety Criteria and Management

Patients who experience hematologic adverse events as described in Table 3, significant clinical laboratory abnormality, or adverse events that may reflect an unfavorable risk-benefit profile may have their dose interrupted at the discretion of the Investigator. The Medical Monitor should be consulted whenever possible prior to decisions for dose interruption.

Patients who withdraw consent and therefore are discontinued from the study should undergo an Early Termination Visit and subsequent Safety Follow-up Visit as appropriate per Section 9.3.1 Patient Withdrawal Procedures, and associated adverse events followed as described in Section 12 Adverse Events.

Hematology parameters will be assessed bi-weekly for the first 4 weeks of the Treatment Period, and every 4 weeks thereafter for the remainder of the study. Prior to dose interruption, hematology parameters should be confirmed with repeat testing at an Unscheduled Visit within 72 hours, except in severe cases (i.e.: neutrophil counts below 0.5 x 10⁹/L) where immediate interruption of dosing is necessary for the safety of the patient. Blood draws confirming dose interruption criteria should occur prior to the first daily dose on the day of draw.

Dose interruption requirements for hematologic abnormalities are provided below. However, less significant changes may warrant clinical intervention and the Investigator should use his/her best clinical judgment when considering a dose interruption whether for singular or aggregate

hematology results above the limits provided in Table 3, or for other clinical signs, symptoms, or considerations that suggest dose interruption is in the best interest of the patient.

Table 3: Selected Hematologic Thresholds for Dose Interruption

Neutrophil Count	Dose Adjustment
Between 0.5 to 1 x 10 ⁹ /L	Interrupt dose until recovered to greater than 1.5 x 10 ⁹ /L and
(Grade 3)	resume dosing at previous dose
Less than 0.5 x 10 ⁹ /L (Grade 4)	Severe case: Interrupt dose immediately and repeat CBC with differential within 72 hours. Recommend hematology consult and contact medical monitor. Permanent discontinuation of treatment should occur upon repeat confirmation of value
Female Hemoglobin Level	Dose Adjustment
Less than 10 g/dL	Interrupt dose until recovered to greater than 10.5 g/dL and resume dosing at previous dose
Male Hemoglobin Level	Dose Adjustment

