Clinical laboratory variables will be presented in 3 ways. First, change from Baseline to each scheduled assessment will be summarized descriptively. Baseline will be defined as the laboratory value obtained before the first dose of study drug on Day 1(Part A, Period 1); if Day 1 values are unavailable, then values obtained at the Screening Visit will be used.

Second, treatment-emergent potentially clinically significant (PCS) laboratory values will be identified. Potentially clinically significant values are defined as those that meet Grade 3 or Grade 4 toxicity criteria from the CTCAE criteria. Treatment-emergent PCS laboratory values are those in which the baseline value is not PCS and the post-baseline value is PCS.

Third, treatment-emergent adverse events that result in dose interruption will also be identified.

The mean change from Baseline to each scheduled assessment will be summarized descriptively by dosing regimen for each clinical laboratory variable specified in this protocol.

The number and percentage of patients with Abnormal, clinically significant laboratory values (per Investigator judgment) and the number and percentage of patients with treatment-emergent PCS laboratory values will be summarized by dosing regimen for each clinical laboratory variable.

Vital Signs

The mean change from Baseline to each scheduled assessment will be summarized descriptively by dose group for each vital sign variable specified in this protocol.

Baseline will be defined as the last vital sign value obtained before the first dose of study drug on Day 1; if Day 1 values are unavailable, then values obtained at the Screening Visit will be used.

Electrocardiogram

The change from Baseline in electrocardiogram intervals (PR, QT, QTcF, QRS, and RR) to each scheduled assessment will be summarized descriptively by dose group.

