- For patients who are ongoing, date of last dose will be imputed as the data cut date.

Summary tables and data listings:

- No preliminary rounding will be performed; rounding will only occur after analysis. Note that for the clinical purposes of moving patients through parts and periods, SALT scores were rounded to the nearest integer prior to determining the SALT  $\leq 20$  criterion.
- Data from patients excluded from an analysis population will be presented in the data listings but will not be included in the calculation of summary statistics, where applicable.

Concert Pharmaceuticals, Inc.  
Statistical Analysis Plan – CP543.2004

- Data from each patient will be separated by a blank line. Within a data listing, if a descriptive item appears line after line (e.g., repetition of a patient number, date, visit, etc.), only the first occurrence will be displayed (e.g., in Listing of Vital Signs, patient number, date and visit will only be displayed on first row when presenting all parameters collected at same visit). Repetition of actual results or outcomes (e.g., adverse events, lab results, vital sign values, etc.) will not be collapsed.
- Data listings will be sorted by treatment, patient, and date and/or time of assessment, as applicable. Data listings may be separated by study part.
- There will be 3 baselines in this study, defined as follows:
  - Part A Period 1 baseline is the last observation obtained on or before the day of dosing of study drug in Part A Period 1.
  - Part A Period 2 baseline is the last observation obtained on or before the day of dosing of study drug in Part A Period 2.
  - Part B baseline is the last observation obtained on or before the day of dosing of study drug in Part B.
- Unless otherwise noted, values reported as greater than or less than some quantifiable limit (e.g., “< 2.0”) will be summarized as using the numeric equivalent in summary tables and figures (e.g. “<2.0” will be analyzed as 2.0). The reported value will be used in listings.

Mock tables and data listings will be provided as attachments to this analysis plan. Minor changes to the mocks after formal SAP approval will not necessitate re-approval unless changes to the text of the SAP are required.

All statistical deliverables will be produced, validated, and reviewed for accuracy/consistency in accordance with [REDACTED] standard operating procedures and the processes described in the statistical validation plan.

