#### **9.5. Clinical Laboratory Evaluation**

Clinical laboratory samples should be collected at the beginning of each clinic visit and just prior to a dose on all Study Visit Days and will be processed by a central laboratory. In the event a

Concert Pharmaceuticals, Inc.  
Statistical Analysis Plan – CP543.2004

patient is unable to attend an in-clinic visit due to COVID-19, clinical laboratory blood draws may be performed by a Home Health Care agency or a local laboratory.

Clinical laboratory variables will be presented in 4 main ways, for each Part/Period of the study. First, change from baseline to each scheduled visit. Only post-baseline values on treatment (i.e., on the same date or prior to last dose of study drug) will be eligible for change from baseline calculations. Summary statistics for the mean and mean change from Part A Period 1 baseline will be reported for Part A Period 1, Part A Period 2, and Part B. The mean and mean change from Part A Period 2 baseline will be reported for Part A Period 2 and Part B. The mean and mean change from Part B baseline will be reported for Part B

Second, treatment-emergent potentially clinically significant (PCS) laboratory values will be identified. Potentially clinically significant values are defined as those that meet Grade 3 or Grade 4 toxicity criteria from the CTCAE criteria (or Grade 2 or higher for platelets). Laboratory values will be graded using CTCAE version 5.0, for those values included. CTCAE grades will be based solely on numeric results and without regard to other symptoms based on clinical judgment. For laboratory parameters whose CTCAE grading is independent of baseline criteria, treatment-emergent PCS laboratory values are those in which the baseline value is not PCS and the post-baseline value is PCS. For laboratory parameters whose CTCAE grading is dependent upon baseline criteria, any post-baseline grading of Grade 3 or Grade 4 (or Grade 2 or higher for platelets) will be considered treatment-emergent. The number and percentage of patients with treatment-emergent PCS laboratory values will be summarized by treatment group and overall for each clinical laboratory variable patient to CTCAE grading. For this analysis, the visit with the highest CTCAE grade value within a window will be selected.

Third, box plots of hemoglobin, platelets, and neutrophils will also be provided with dose interruption limits included as reference lines (see Protocol Section 10.2.1).

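### For laboratory parameters graded independently of baseline, SAP 9.5 leaves worsening from one PCS grade to a higher one out of the treatment-emergent PCS tables, and does not name the baseline for Period 2 and Part B

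*SAP*

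**What the plan says.** Protocol Section 13.4.5 sets the category: "Potentially clinically significant values are defined as those that meet Grade 3 or Grade 4 toxicity criteria from the CTCAE criteria". SAP Section 9.5 keeps this and lowers the platelet threshold to Grade 2.

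SAP 9.5 then gives two rules for when a PCS value is treatment-emergent.

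- The first opens with "For laboratory parameters whose CTCAE grading is independent of baseline criteria" and continues: "treatment-emergent PCS laboratory values are those in which the baseline value is not PCS and the post-baseline value is PCS".
- The second reads "For laboratory parameters whose CTCAE grading is dependent upon baseline criteria, any post-baseline grading of Grade 3 or Grade 4", repeats the Grade 2 threshold for platelets, and calls every such value treatment-emergent. It sets no condition on the baseline grade.

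The SAP does not list which parameters fall under which rule.

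On baselines, SAP Section 4 states: "There will be 3 baselines in this study, defined as follows". One of the definitions is that "Part A Period 2 baseline is the last observation obtained on or before the day of dosing" in that period; Part B has a parallel definition. SAP 9.5 presents laboratory data by Part/Period and names the baseline for each mean-change summary, but names none for the PCS summary. Protocol 13.4.5 defines a single laboratory baseline, the value before the first dose on Day 1 of Part A Period 1, with Screening as fallback.

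SAP Appendix 15.4 lists treatment-emergent PCS tables for hematology, chemistry and lipids (14.3.4.4 to 14.3.4.6) for each Part/Period. It lists no laboratory shift or grade-worsening table.

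**The concern.** Because all PCS grades form one category, the first rule records only the crossing of the PCS threshold. Once the reference value is PCS, further deterioration under that rule cannot be counted.

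This matters more in Period 2 and Part B than at study entry. If those periods use their own baselines, the reference is a value from a patient already in the trial. The PCS tables are the SAP's summary of laboratory toxicity by numeric grade. They could show no event in a period for a patient who reached a higher grade in that period. Since the baseline is not named, two programmers could also produce different counts from the same data, both consistent with the SAP.

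**Working it through.** The documents give no figure on this point to reproduce. The check applies the two rules to every possible grade change, then to the possible baselines.

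**1. The rules as logic.** Let b be the baseline grade and p the post-baseline grade, each 0 to 4.

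- Baseline-independent: counted if b is not PCS and p is PCS.
- Baseline-dependent: counted if p is PCS, whatever b is.

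**2. Worsening pairs under the baseline-independent rule.**

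- PCS at Grade 3 or higher: three pairs end at Grade 3 (b = 0, 1, 2) and four at Grade 4 (b = 0, 1, 2, 3), so 3 + 4 = 7. Six are counted. The one missed is 3 to 4.
- PCS at Grade 2 or higher, which concerns platelets only if they fall under this rule: 2 + 3 + 4 = 9 pairs. Three are missed: 2 to 3, 2 to 4, and 3 to 4.

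**3. Effect of the baseline.** Take a patient at Grade 3 at the Period 2 baseline who reaches Grade 4 in Period 2.

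| Rule | Period 1 baseline | Reference used in Period 2 | Counted in Period 2 table |
|---|---|---|---|
| Independent | not PCS | Period 1 | yes |
| Independent | not PCS | Period 2 | no |
| Independent | PCS | either | no |
| Dependent | either | either | yes |

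In the second row, the Grade 3 value meets the rule in the Period 1 table, but the later Grade 4 is not shown in Period 2. The same logic applies to Part B.

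**4. Can a baseline be PCS?**

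- Period 2 entry depends on SALT at Week 24, and no laboratory limits are stated (Protocol 8.1, 10.1). Week 24 also serves as Period 2 Day 1 (Protocol Table 1, footnote 3), so the baseline follows 24 weeks on 8 mg or 12 mg BID.
- Part B Day 1 is the last Period 2 visit and assessments are not repeated (Protocol Table 2, footnote 2). That baseline follows a reduced dose or placebo.
- At Period 1 entry, Protocol 9.2 gives numeric limits for several tests but none for lipids, creatine kinase, amylase or lipase. Lipids are first drawn on Day 1. If any of these fall under the baseline-independent rule, the gap can arise whichever baseline is used.

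**5. Illustration.** Protocol Table 3 prints neutrophil grades as absolute counts: 0.5 to 1 x 10⁹/L is Grade 3 and below 0.5 is Grade 4. In hypothetical records using the Period 2 baseline, 0.9 falling to 0.4 counts 0, while 1.6 falling to 0.9 counts 1. With a non-PCS Period 1 baseline as reference, the first record counts 1.

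**6. Size.** The documents give no rate of PCS values at Week 24 or at Part B entry. With about 25 patients planned per Period 2 arm, one uncounted patient is 1/25 = 4 percentage points.

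**The case against.** The strongest reply is that the gap depends on a baseline the SAP does not prescribe for PCS. The only laboratory baseline that either document places beside the PCS rule is Period 1 Day 1 (Protocol 13.4.5), and SAP Section 13 lists no change to it. With that baseline the neutrophil record is counted, and the Screening exclusion for neutrophils at or below 1.5 x 10⁹/L makes a PCS Period 1 value unlikely. This stands as a reason not to treat the period baseline as settled. It does not remove the ambiguity: the SAP defines three baselines, reports laboratory data by Part/Period, and takes precedence over the protocol where they differ (SAP Section 2). Nor does it help parameters without a numeric entry limit.

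A reader might infer that no laboratory value can be treatment-emergent after a PCS baseline. The documents do not support that, because the baseline-dependent rule counts any post-baseline Grade 3 or 4. Platelets are uncertain: of the two rules, only the baseline-dependent one names them, and under it a change from Grade 2 to Grade 3 or 4 is counted.

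A reader might also infer that such a patient is never counted anywhere. That is not supported either. A Grade 3 value that arose earlier can count in the earlier period's table. The Grade 4 value would be in the laboratory listings and abnormal-value outputs. If judged clinically significant, or important enough to require interruption, it is also an adverse event (Protocol 12.1). What remains is that the abnormal-value tables are not described as graded, adverse event capture largely depends on investigator judgment, and the PCS grading is purely numeric.

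The interruption thresholds in Protocol Table 3 and the weekly monitoring during interruption should make the neutrophil path uncommon. Counting threshold crossings is also a coherent choice carried over from the protocol, but the SAP gives no reason for treating the two groups of parameters differently.

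**Conclusion.** The point holds as a minor gap and an ambiguity. For baseline-independent parameters, worsening from one PCS grade to a higher one is missing from that Part/Period's PCS table whenever the reference value is PCS: one of seven worsening pairs at the Grade 3 threshold. No planned shift table shows it. In Period 2 and Part B, how often this happens depends on a baseline that SAP 9.5 leaves unnamed.

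The conclusion assumes that some parameters, such as neutrophils, fall under the baseline-independent rule, and that PCS values sometimes occur at the reference visit. The number of patients cannot be computed from the documents and is probably small. All safety summaries are descriptive, so no test is affected, and the underlying values remain visible in other outputs.

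**What to change.** In SAP 9.5:

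1. Name the baseline used for the PCS rule in each Part/Period. If it differs from Period 1 Day 1, record the change from Protocol 13.4.5 in SAP Section 13.
2. For baseline-independent parameters only, define treatment-emergent PCS as a post-baseline PCS value with a CTCAE grade higher than the grade at that baseline. This keeps every pair now counted and adds the missed ones: 7 of 7 at the Grade 3 threshold, and 9 of 9 at a Grade 2 threshold.
3. Leave the baseline-dependent rule unchanged. Extending the new wording to it would narrow that rule and could lower its counts.
4. State which rule applies to platelets.

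SAP 9.6.1 borrows the PCS definition for vital signs, so its cross-reference should be checked.

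The cost is a few sentences and one derivation line; the highest grade in each window is already selected for this analysis. The downside is that, for a given baseline, PCS counts may rise slightly.

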## **9.6. Vital Signs, Physical Findings, and Other Observations Related to Safety**

### **9.6.1. Vital Signs**

Vital signs will be measured after the patient has been in a supine or semi-supine position for at least 5 minutes and will include blood pressure, pulse rate, respiratory rate, and temperature.

Height will only be measured at the Screening Visit in Part A Period 1. Weight and vital signs will be measured according to the Schedule of Assessments (Appendix 15.2). Weight and height will be used to calculate the patient's body mass index at Screening.

The mean change from Part A Period 1 baseline to each scheduled assessment will be summarized descriptively by treatment group and overall for each vital sign variable specified in the protocol.

The number and percentage of patients with at least 1 PCS vital sign value, defined as for laboratory values in Section 9.5, will be summarized descriptively by treatment group and overall. A listing of vital signs by patient will also be provided.

### **9.6.2. Physical Examinations**

A complete physical examination will consist of an examination of all major organ systems to include, but not be limited to, chest auscultation, abdominal auscultation and palpation, head, eyes, ears, nose and throat. An assessment for active signs and symptoms of infection including tuberculosis and skin examinations for non-melanoma skin cancers will be performed.

Evaluation for progressive multifocal leukoencephalopathy symptoms such as facial droop, general weakness, clumsiness, trouble speaking, personality changes, memory problems, and vision changes will be assessed.

Additionally, an assessment for the presence or absence of nasal hair will be performed during complete physical exams. Presence or absence of nasal hair will be summarized at baseline, Week 24 (Part A Period 1), Week 48 (Part A Period 2), and Week 24 (Part B). The presence or absence of nasal hair will be summarized as counts and percentages by treatment group and visit for the Safety Population, for each Part/Period of the study.

Brief physical examinations will include assessment for active signs and symptoms of infection, including tuberculosis, skin examinations for non-melanoma skin, and an evaluation for PML symptoms such as facial droop, general weakness, clumsiness, trouble speaking, personality changes, memory problems, and vision changes. Brief physical examinations will be performed according the Schedule of Events (Appendix 15.2).

A listing of the date and type of physical examinations performed will be provided. The listing will include presence or absence of nasal hair. Deteriorations from baseline on physical examination will be coded as adverse events and summarized as such.

### **9.6.3. Other Safety Measures**

#### **9.6.3.1. 12-Lead Electrocardiogram**

Twelve-lead electrocardiograms (ECG) will be performed according to the Schedule of Assessments (Appendix 15.2) after the patient has rested in a supine or semi-supine position for at least 5 minutes. Individual parameters including heart rate, PR, QT, QTcF (Frederica's correction), QRS, and RR intervals will be collected. If a patient is unable to attend an in-person clinic visit due to COVID-19, an ECG may not be performed. Missed assessments will be recorded in the eCRF as due to COVID-19.

The mean change from Part A Period 1 baseline to each scheduled assessment will be summarized descriptively by treatment group and overall for each ECG variable specified in the protocol, for each Part/Period of the study.

A listing of ECG results will be provided. A listing of abnormal ECG findings will also be provided.

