## 9. SAFETY EVALUATION

### 9.1. Overview of Safety Analysis Methods

All safety summaries will be descriptive with no statistical hypothesis testing and based on the Safety Population. Patients will be summarized according to the study drug received (i.e., as treated), should it differ from the randomized treatment arm. Safety assessments will be summarized by treatment group and overall, for each Part/Period of the study. All safety endpoints will be listed in by-patient data listings.

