Table	14.3.5.1.1	Vital Signs Summary — Part A Period 1	Safety Population	
Table	14.3.5.1.2	Vital Signs Summary — Part A Period 2	Safety Population	
Table	14.3.5.1.3	Vital Signs Summary — Part B	Safety Population	
Table	14.3.5.2.1	Presence or Absence of Nasal Hair by Treatment Group and Visit — Part A Period 1	Safety Population	Y
Table	14.3.5.2.2	Presence or Absence of Nasal Hair by Treatment Group and Visit — Part A Period 2	Safety Population	Y
Table	14.3.5.2.3	Presence or Absence of Nasal Hair by Treatment Group and Visit — Part B	Safety Population	
Table	14.3.5.3.1	12-Lead Electrocardiogram Summary — Part A Period 1	Safety Population	
Table	14.3.5.3.2	12-Lead Electrocardiogram Summary — Part A Period 2	Safety Population	
Table	14.3.5.3.3	12-Lead Electrocardiogram Summary — Part B	Safety Population	
Table	14.3.5.4.1	Summary of Missing or Remote Visits Related to COVID-19 by Treatment Group — Part A Period 1	Safety Population	
Table	14.3.5.4.2	Summary of Missing or Remote Visits Related to COVID-19 by Treatment Group — Part A Period 2	Safety Population	

Concert Pharmaceuticals, Inc.  
Statistical Analysis Plan – CP543.2004

Type	Number	Title	Population	For abbreviated report?
Table	14.3.5.4.3	Summary of Missing or Remote Visits Related to COVID-19 by Treatment Group — Part B	Safety Population	
Figure	14.1.1.1	Summary of Patient Disposition — CONSORT Diagram — Part A Overall	All Screened Patients	Y
Figure	14.1.1.2	Summary of Patient Disposition — CONSORT Diagram — Part A and Part B	All Screened Patients	
Figure	14.1.2.1	Kaplan-Meier Plot for Time to Treatment Discontinuation — Part A Period 1	Safety Population	Y
Figure	14.1.2.2	Kaplan-Meier Plot for Time to Treatment Discontinuation — Part A Period 2	Safety Population	Y
Figure	14.1.2.3	Kaplan-Meier Plot for Time to Treatment Discontinuation — Part B	Safety Population	
Figure	14.2.1.1	Patients Achieving Loss of Regrowth Maintenance (SALT Score $>20$ ) or Response (SALT Score $\leq 20$ ) by Treatment at End of Part A Period 2 — Part A Period 2	Efficacy Population	Y
Figure	14.2.2.1.1	Responders (SALT Score $\leq 20$ ) by Treatment across Time — Part A Period 1	Efficacy Population	Y
Figure	14.2.2.1.2	Loss of Regrowth Maintenance (SALT Score $>20$ ) by Treatment across Time — Part A Period 2	Efficacy Population	Y
Figure	14.2.2.1.3	Responders (SALT Score $\leq 20$ ) by Treatment across Time — Part A Period 2	Efficacy Population	Y

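### Vital-sign and ECG change in Period 2 and Part B is summarised only from the Period 1 baseline, so change carried in from Period 1 is not separated from later change

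*SAP*

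**What the plan says.** SAP section 4 defines three baselines, one each for Part A Period 1, Part A Period 2 and Part B. The second is given as: "Part A Period 2 baseline is the last observation obtained on or before the day of dosing of study drug in Part A Period 2".

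For ECG, SAP 9.6.3.1 states "The mean change from Part A Period 1 baseline to each scheduled assessment will be summarized descriptively by treatment group and overall for each ECG" and the sentence ends "variable specified in the protocol, for each Part/Period of the study". The Period 1 baseline is the only reference named, and it is carried explicitly into Period 2 and Part B.

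For vital signs, SAP 9.6.1 states "The mean change from Part A Period 1 baseline to each scheduled assessment will be summarized descriptively by treatment group and overall". That section does not list the Parts. SAP 9.1 does so for safety data in general: "Safety assessments will be summarized by treatment group and overall, for each Part/Period of the study". SAP 15.4 lists Table 14.3.5.1.2, "Vital Signs Summary — Part A Period 2", and a Part B counterpart, 14.3.5.1.3. The matching ECG tables are 14.3.5.3.2 and 14.3.5.3.3. None of these titles names a baseline. Under SAP section 4, the Period 2 and Part B columns are the treatment sequences, for example 8 mg BID followed by placebo.

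Laboratory values are handled differently. SAP 9.5 keeps the Period 1 baseline and adds "The mean and mean change from Part A Period 2 baseline will be reported for Part A Period 2 and Part B", and it also adds change from the Part B baseline for Part B. SAP 8.4.1 does the same for SALT. It omits only relative change from the Period 2 baseline, and explains that this baseline can be zero.

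**The concern.** Period 2 exists to show what follows dose reduction or discontinuation, and Part B what follows re-treatment. A reader of the Period 2 vital-sign or ECG table will want to know what happened after re-randomisation. The planned figure answers a different question: where patients stand relative to Day 1, before any study drug.

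Both re-randomised arms within a dose group arrive with 24 weeks on that dose behind them. A shift in pulse, blood pressure or an ECG interval that arose in Period 1 and simply persisted would appear under the placebo sequence. One that disappeared after discontinuation would leave little or nothing to see. What is at stake is a descriptive safety reading in the final report.

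**Working it through.** The plan states no figure on this point, so there is nothing to reproduce. The check is an identity applied to the SAP text, followed by a comparison of sections.

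**Inputs.** The baselines are those of SAP section 4. The references used are those of SAP 9.5, 9.6.1 and 9.6.3.1. The arms and numbers come from Protocol 13.1: about 170 patients on 8 mg BID and 130 on 12 mg BID, about 50 Responders per dose group, and about 25 per Period 2 arm. No vital-sign or ECG effect is given, so a mean carried-in change d of 2, 5 or 10 units is assumed for illustration.

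**Identity.** Change from Period 1 baseline = change carried in from Period 1 + change since the Period 2 baseline. If a fraction r of d reverses in Period 2:

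- shown from the Period 1 baseline: d - r × d
- shown from the Period 2 baseline: -r × d

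| Reversal r | From Period 1 baseline (d = 2 / 5 / 10) | From Period 2 baseline (d = 2 / 5 / 10) |
|---|---|---|
| 0 (persists) | +2 / +5 / +10 | 0 / 0 / 0 |
| 0.5 | +1 / +2.5 / +5 | -1 / -2.5 / -5 |
| 1 (full) | 0 / 0 / 0 | -2 / -5 / -10 |

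**Part B.** Suppose d reverses fully in Period 2 and returns on re-treatment. Change is then +d from the Period 1 baseline, d - d = 0 from the Period 2 baseline, and +d from the Part B baseline. If instead d never reversed and nothing happened in Part B, the three figures are +d, 0 and 0. Only the Part B baseline tells the two histories apart.

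**Do other planned summaries separate the parts?** The Period 1 tables are laid out by 8 and 12 mg over all treated patients. Only about 50/170 = 29% and 50/130 = 38% of them are expected to enter Period 2, and each group is then split 1:1. Those tables therefore do not give the carried-in change by Period 2 arm. The Period 2 tables might contain a Week 24 row, since that visit doubles as Period 2 Day 1 (Protocol Table 1, footnote 3). Neither the titles nor the text says so, and the table mock-ups are not among the documents available. Even with such a row, subtracting arm means would be inexact, because patients leave Period 2 when they meet the LOM criterion and later rows rest on fewer patients. No summary that the SAP describes isolates the within-period change. The by-patient listings (16.2.10.1.x and 16.2.10.2.x) do hold the values needed to derive it by hand.

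**Are the data there?** Protocol Table 1 schedules both vital signs and ECG at Week 24, so the Period 2 baseline is already collected. Period 2 ECGs are scheduled only at Weeks 36 and 48, and Part B Day 1 repeats no assessments (Protocol Table 2, footnote 2). A patient who meets LOM at another visit may therefore have a Part B ECG baseline from an earlier date. Footnote 14 of Protocol Table 1 asks for the Period 2 safety assessments before Part B drug is dispensed. It does not make clear whether that includes an ECG at a visit where none is scheduled.

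**The case against.** The strongest reply is that the Period 1 baseline is a deliberate and proper choice. Protocol 13.4.5 sets the vital-sign baseline before the first dose on Day 1 and defines no later one for ECG, so the SAP follows the protocol. For cumulative safety the untreated value is the natural reference, and a return to it on placebo is correctly reported as about zero. The column labels show the whole sequence, so the earlier dose is not hidden. All of this stands. It means the Period 1 summary is not an error and should be kept. It does not explain why laboratory values, under the same protocol section, were given the later baselines and these measures were not.

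The consequence is also limited. Adverse events are attributed to each Part or Period, and counts of potentially clinically significant vital signs and a listing of abnormal ECGs are planned. The vital-sign and ECG tables are not marked for the abbreviated NDA report. These points hold down the importance, but none of them supplies a mean change since re-randomisation.

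A reader might infer three stronger things, and the documents support none of them:

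- **That the table will give false signals or miss real ones at some rate.** Safety summaries are descriptive, and no interval or test is specified for these variables. Any such rate would score an unplanned analysis on effect sizes and correlations that the documents do not give.
- **That the within-period change cannot be recovered.** The listings allow it to be derived, and the table layouts are not available to rule out a Week 24 row.
- **That the primary objective is compromised.** Its endpoints are based on SALT, which does have a Period 2 baseline summary.

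**Conclusion.** The point holds as a gap in the planned summaries, worth closing because it is cheap. For vital signs and ECG, the only mean change that the SAP specifies in Period 2 and Part B merges the Period 1 shift with everything after it. Only a full reversal reads as no change; a partial one reads as a smaller residual. The size equals whatever shift patients carry in at Week 24. The documents give no value for it, and if it is negligible the two baselines agree on average. The conclusion rests on the identity and on the wording of SAP 9.5, 9.6.1 and 9.6.3.1, not on the illustrative units.

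**What to change.** In SAP 9.6.1 and 9.6.3.1, keep change from the Part A Period 1 baseline and add, on the model of 9.5:

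- mean and mean change from the Part A Period 2 baseline, for Period 2 and Part B;
- mean and mean change from the Part B baseline, for Part B.

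Name the baseline in the titles of Tables 14.3.5.1.x and 14.3.5.3.x, as most of the laboratory change tables already do. State that change from the Period 2 baseline is the figure to use when describing vital signs and ECG after dose reduction or discontinuation. Footnote any Part B ECG baseline that predates the LOM visit.

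The cost is a sentence or two in each of two SAP sections and a few extra table panels from data already scheduled. No protocol change and no new assessment is needed. The downside is more output and some Part B ECG baselines older than the LOM visit, which the footnote makes visible.
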